5.2.3 Part C

Approx. 15 patients (including adults and adolescents $\geq 12 - \langle 18 \rangle$ years old) will be randomized in double-blind manner to one of the following 3 parallel arms: 3 mg/kg or 5 mg/kg or 10 mg/kg of MCS110 in a ratio of approximately 2:2:1.

In case a lower dose is identified to be at least as efficacious as 10 mg/kg after 3 doses, additional 4 patients may be enrolled in this lower dose group and randomized in an open label fashion to a total of approximately 10 patients.

Table 5-1 Treatment arms in Part C

Treatment	Double-blind	Potential open label extension
3 mg/kg	n ~6	n ~4*
5 mg/kg	n ~6	n ~4*
10 mg/kg	n ~ 3	n=0

*Either 3 or 5 mg/kg may be expanded.

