9.4.4 Supportive analyses

Part A

As a supportive analysis, log ratio to baseline of tumor volume at week 4 may be subjected to an Analysis of Covariance (ANCOVA) model. The model will include log transformed tumor volume at baseline and a factor for treatment. Point estimates and 95% confidence interval will be calculated for each treatment group and for the difference of means between treatment groups. Results will then be transformed back to the original scale.

Part B

To study the time course of tumor volume reduction from baseline, a repeated measures ANCOVA model may be fit by resetting the tumor volume at week 4 as baseline for patients in treatment group 2 and the assessment time will be adjusted accordingly. The model will include tumor volume at baseline and assessment time (in month) as fixed effects. Standard fit statistics will be used to determine the best variance-covariance structure. Point estimates and 95% confidence interval will be calculated at each assessment time-point and between different assessment time-points.

Part C

As a supportive analysis, log ratio to baseline of tumor volume at week 4 may be subjected to an Analysis of Covariance (ANCOVA) model. The model will include log transformed tumor volume at baseline and a factor for treatment. Point estimates and 95% confidence interval will be calculated for each treatment arm and for the difference of means between treatment groups. Results will then be transformed back to the original scale.

Parts A, Part B and Part C

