7.1 Data post-surgery will not be used for primary analysis - Primary Endpoint

Part A, B and C pooled for weeks 1 to 4 (referred as 'Part A*' hereafter)

The tumor size (volume) as assessed by MRI technique up to and including week 4 will be the primary measure of efficacy. This data will be listed as collected.

Consolidated tumor volume will be calculated as the geometric mean from two readers. Summary statistics of the consolidated tumor volume will be presented by treatment and visit time. The tumor volume measured at screening is treated as baseline. The percent change and absolute change from baseline of the consolidated tumor volume will be summarized in the same fashion. Waterfall plot on percent change from baseline after 4 weeks will be produced. The tumor size at baseline and after 4 weeks will be log transformed. The log ratio to baseline of the tumor size (change from baseline of log transformed volume) will be the primary measure of efficacy for the single dosing part of the study (Part A*).

The analysis of the primary endpoint will quantify the accumulation of evidence about the treatment effect as patients complete their 4 week treatment. The evidence will be summarized in the posterior distributions of the treatment group means and their differences. These posterior distributions will be updated after certain patients complete the 4 week treatment.

For the analysis, the distributional model for the observed data (log ratio) will be the normal model with unknown parameters μ and σ , with μ being the parameter of primary interest (treatment mean) and σ representing the sampling error. This model will be applied to each MCS110 dose group separately. Little prior information is available for these parameters and therefore non-informative prior distributions will be placed on them. For μ a normal prior distribution centered at 0 (no treatment effect) will be used with large standard deviation, and for σ a uniform (0,2) prior distribution.

The model is formally described below, LR being the log ratio of tumor volume:

Likelihood

$$LR_i \sim N(\mu, \sigma)$$

with

$$\mu = \mu_p \text{ for observations from placebo group}$$

$$\mu = \mu_m \text{ for observations from MCS110 group}$$

Prior distributions on treatment means μ 's

$$\mu_p \sim N(0, 0.3)$$

$$\mu_m \sim N(0, 10) \text{ * i.e. Neutral prior or}$$

$$\mu_m \sim N(0, 0.3) \text{ * i.e. Skeptical prior}$$

Prior distributions on sigma

$$\sigma \sim \text{Uniform}(0,2)$$

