The same model as above will also be applied to compare the efficacy of the 3 mg/kg and 5 mg/kg to the 10 mg/kg dose (instead of Placebo).

Part B and C (referenced as Part B* hereafter)

Part B includes all data from multiple dosing Parts. In Part B, treatment group 1 = MCS110 throughout the trial, treatment group 2 = Placebo for the first dose and MCS110 from the second dose. In Part C, treatment arm 1 = MCS110 3 mg/kg, treatment arm 2 = MCS110 5 mg/kg, treatment arm 3 = MCS110 10 mg/kg, for patients in treatment arms 1 and 2 that switch to 10 mg/kg after 3 doses, they will be included in their original treatment group for the first 3 doses and will added in a separate group after that (4= MCS110 3 mg/kg for 3 doses and 10 mg/kg afterwards and 5= MCS110 5 mg/kg for 3 doses and 10 mg/kg afterwards), no re-calculation of baseline will occur for the people who change treatments.

Tumor volumes will be listed at each MRI assessment timepoint till the end of the study by treatment groups.

Part B*: MCS110 data only, by including data starting from the 1st dose of MCS110 in all treatment groups of Parts B and C. More specifically, for Part B treatment group 2, the measurement right before patients receiving the first dose of MCS110 (2nd dose from screening) will be treated as the new baseline and assessment time-points will be adjusted accordingly. Summary statistics of the consolidated tumor volume for the raw values, percent change and absolute change from baseline.

Arithmetic mean (+/-) SE on percent change from baseline vs time plot will be produced for Part B*. Waterfall plot of the maximum reduction until 8 Weeks after last dose will be produced in regards of number of doses received.

Overall Time to complete tumor ablation will be summarised up to the primary endpoint (8 weeks after the last MCS110 dose), along with a summary of overall time to $\geq 50\%$, and $\geq 80\%$ ablation. The number and frequency of patients reaching each level will also be included in the summary.

Overall Time to complete ablation is the time (in weeks) - from first MCS110 dose to the first time when there is no tumor detected. Overall time to $\geq 50\%$, and $\geq 80\%$ ablation is the time from first MCS110 dose to reach maximum ablation of [50%, 80%) and [80%, complete) respectively.

Part C

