7.1.2 Supportive analyses

Part A, Part B and Part C pooled for weeks 1 to 4 (Part A*)

As a supportive analysis, log ratio to baseline of tumor volume at week 4 may be subjected to an Analysis of Covariance (ANCOVA) model. The model will include log transformed tumor volume at baseline and a factor for treatment. Point estimates and 95% confidence interval will be calculated for MCS110 and Placebo separately, and for the difference of means between MCS110 and Placebo. Results will then be transformed back to the original scale.

Part B*:

To study the time course of tumor volume reduction from baseline, a repeated measures ANCOVA model on log ratio to baseline will be fit by resetting the tumor volume at week 4 as baseline for patients in treatment group 2 and the visit number will be adjusted accordingly. The model will include log tumor volume at baseline and visit as fixed effects. Standard fit statistics will be used to determine the best variance-covariance structure. Point estimates and 95% confidence interval will be calculated at each visit. Baseline adjusted tumor volume (+/- SE) over time will be plotted.

Part C:

As a supportive analysis, log ratio to baseline of tumor volume at week 4 may be subjected to an Analysis of Covariance (ANCOVA) model. The model will include log transformed tumor volume at baseline and a factor for treatment. Point estimates and 95% confidence interval will be calculated for each treatment arm and for the difference of means between treatment groups. Results will then be transformed back to the original scale.

The statistical analysis will also be provided by age group (<18 years and ≥18 years).

Parts A, B and C :

A dose-time-response model (Lange and Schmidli 2015) will be used to analyze tumor response data (log ratio to baseline of tumor volume) from Parts A, B, and C. The following equation will be used for the latent concentration $C(t)$ of a patient who receives K doses with dose D_k received at time t_k , $k=1, \dots, K$:

$$C(t) = \sum_{k=1}^q \frac{D_k \theta_1}{\theta_1 - \theta_2} \left\{ \exp \left[-\theta_2 \left(t - \sum_{j=0}^{k-1} \delta_j \right) \right] - \exp \left[-\theta_1 \left(t - \sum_{j=0}^{k-1} \delta_j \right) \right] \right\}$$

where $\delta_0=t_1$, $\delta_j=t_{j+1} - t_j$ for $j=1, \dots, K-1$ and $q \in \{1, \dots, K - 1\}$ is such that $t_q < t \leq t_{q+1}$ and $q=K$ if $t > t_K$.

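### The supportive Part A\* and Part B\* ANCOVAs in SAP 7.1.2 average over MCS110 doses, and after week 12 the Part B\* visit means are also mixed with response-driven escalation

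*SAP*

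**What the plan says.** SAP 7.1 defines Part B\* as "MCS110 data only, by including data starting from the 1st dose of MCS110 in all treatment groups of Parts B and C". SAP 7.1.2 then specifies a repeated-measures ANCOVA of the log ratio to baseline for this data set, to describe the time course of tumour volume: "The model will include log tumor volume at baseline and visit as fixed effects". Dose, arm and switch group are not in the model.

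The corresponding model in Protocol 9.4.4 is for Part B only: "The model will include tumor volume at baseline and assessment time (in month) as fixed effects". MCS110 was given at 10 mg/kg throughout Part B, so that model needed no dose term. Part C randomises patients to "3 mg/kg or 5 mg/kg or 10 mg/kg of MCS110 in a ratio of approximately 2:2:1". Lower-dose patients who tolerate the drug but have less than 45% reduction at week 12 move to 10 mg/kg (Protocol 5.5.5.2, SAP 2.4). For those patients SAP 7.1 says, under Part B and C, that "they will be included in their original treatment group for the first 3 doses and will added in a separate group after that". This grouping does not enter the Part B\* model.

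The Part A\* ANCOVA in SAP 7.1.2 uses weeks 1 to 4 of all three parts. It has a treatment factor whose levels are not listed, and its outputs are binary: "Point estimates and 95% confidence interval will be calculated for MCS110 and Placebo separately", plus their difference. For the Bayesian model on the same data, SAP 7.1 says instead: "This model will be applied to each MCS110 dose group separately".

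**The concern.** Widening the data from Part B to Parts B and C changed what the model estimates, but the terms stayed the same. A visit mean without dose is an average over whichever doses the patients at that visit received. The weights come from the sizes of the parts, the 2:2:1 ratio and an optional open-label extension, so the target quantity moves with an enrolment decision.

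Part C asks whether lower doses match 10 mg/kg. Reading the pooled estimate as the effect of MCS110 at any one dose presumes that they do. After week 12 there is a second problem in Part B\*: poorly responding lower-dose patients are escalated, so the dose mix changes between visits for a reason tied to the outcome. The visit effect, which is the purpose of this model, then combines time with escalation.

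In Part A\* no one has switched yet. The issue there is that the supportive contrast estimates a different quantity from the per-dose model it is meant to support.

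**Working it through.** **Inputs**
- Part A: seven patients treated (Protocol 3.2.1), two of them on placebo (SAP 7.1.2), so 5 on MCS110. Protocol 3.5.1 also uses 5 as the Part A denominator.
- Part B: 11 patients on MCS110 (Protocol Section 1, Study CMCS110X2201), 3 of them with placebo as first dose (SAP 7.1.2).
- Part C: about 6, 6 and 3 at 3, 5 and 10 mg/kg, plus 4 in one lower-dose arm if extended (Protocol Table 5-1). The protocol reports 18 patients in Part C but no split by dose, so planned counts are used, without and with the extension.

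**The plan's own counts.** At 10 mg/kg: 5 + 11 + 3 = 19. Placebo: 2 + 3 = 5. Both match SAP 7.1.2.

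**Dose mix**

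| Data set | 10 mg/kg | Lower doses | Lower share | With extension |
|---|---|---|---|---|
| Part A\* | 5 + 8 + 3 = 16 | 12 | 12/28 = 43% | 16/32 = 50% |
| Part B\* | 11 + 3 = 14 | 12 | 12/26 = 46% | 16/30 = 53% |

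**Effect of pooling.** Without a dose term, the model estimates approximately the patient-weighted mean log ratio. The pooled reduction is 1 − exp[(n10 ln r10 + nL ln rL)/(n10 + nL)], where r is volume relative to baseline. The documents give 40% for 10 mg/kg at one month (expected, Protocol 9.13) and about 50% after three doses (Protocol 1.4). They give no lower-dose effects; those below are assumed.

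Part B\*, week 12, lower doses at 30%: exp[(14 ln 0.5 + 12 ln 0.7)/26] = 0.584, a reduction of 41.6%.

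| Part B\* week 12, lower-dose reduction | 50% | 45% | 30% | 15% |
|---|---|---|---|---|
| Pooled estimate | 50.0% | 47.8% | 41.6% | 36.1% |
| With extension | 50.0% | 47.4% | 40.2% | 33.6% |

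| Part A\* week 4, lower-dose reduction | 40% | 30% | 20% | 10% | 0% |
|---|---|---|---|---|---|
| Pooled estimate | 40.0% | 35.9% | 32.1% | 28.6% | 25.3% |
| With extension | 40.0% | 35.2% | 30.7% | 26.5% | 22.5% |

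**Mix after week 12.** The share of Part B\* patients on 10 mg/kg is (14 + 12s)/26, where s is the fraction of lower-dose patients who switch (assumed). It is 54% before the switch, and 65%, 77%, 88% or 100% for s = 25%, 50%, 75% or 100%.

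**Price of separating doses in Part A\*.** Take SD = 0.2 × √2 = 0.283, one of the scenarios in Protocol 9.13, and SE = SD × √(1/n1 + 1/n2):
- pooled MCS110 against placebo (28 vs 5): 0.137
- 10 mg/kg against placebo (16 vs 5): 0.145, and 0.1449/0.1373 = 1.055, about 6% more
- a 6-patient lower-dose arm against placebo (6 vs 5): 0.171

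**The case against.** The strongest reply is that dose is analysed elsewhere. A reader might infer from these two models that the plan cannot compare doses; the documents do not support that. The Bayesian week-4 model is run per dose and also compares 3 and 5 mg/kg with 10 mg/kg. A Part C week-4 ANCOVA gives estimates by arm and differences between arms. Tumour volumes are summarised by arm at every MRI. The dose-time-response model uses each dose and its timing, so it accommodates switching. Both criticised models are labelled supportive, and the Part A\* one is optional. All of this stands. What remains is that the Bayesian model and the Part C ANCOVA stop at week 4, so the only modelled time course by dose beyond it is the parametric dose-time-response model.

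The Part A\* treatment factor could be coded by dose. That is fair, but the listed outputs still collapse to MCS110, placebo and one difference.

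The size is uncertain and may be nil. This also stands. With a standard error of 0.137, a 40% effect against placebo has a 95% interval of about 21% to 54%, so a shift of a few points lies well inside the noise.

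The SAP's five groups (three doses and two switch groups) might seem the natural factor to add at all visits. They are not. Switching is decided by the week-12 response, so at earlier visits the unswitched lower-dose groups would be selected for good response and the switched groups for poor response. The adult Part C schedule has up to nine post-baseline MRI visits, so five groups by nine visits is 45 cell means from about 26 patients.

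**Conclusion.** The point holds for these two supportive models only. As written, the Part B\* repeated-measures ANCOVA and the Part A\* ANCOVA estimate an effect averaged over a dose mix fixed by part sizes, with about 46% and 43% of patients on lower doses. After week 12 the Part B\* visit means also carry response-driven escalation.

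The displacement from the 10 mg/kg effect depends on lower-dose effects that the documents do not give. It is zero if all doses are equally effective. Under the assumed values it is about 8 points at week 12 (50% against 41.6%, lower doses at 30%) and about 4 points at week 4 (40% against 35.9%, lower doses at 30%). A reader might conclude that the pooled intervals are bound to be wrong, or that they describe no dose actually given. Neither follows, because with a flat dose response they would be valid for every dose. The plan simply should not build that assumption into a model in a study part that tests it.

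**What to change.** Amend SAP 7.1.2.

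- **Part B\*, visits to week 12:** add initial dose (3, 5, 10 mg/kg) and dose-by-visit. With MRI at weeks 4, 8 and 12 this is 3 × 3 = 9 cell means instead of 3.
- **Part B\*, switch status:** do not use it as a factor at visits before the switch.
- **Part B\*, after week 12:** either keep patients by initial dose, described as a regimen that allows escalation, or show the switch groups descriptively only and label them as response-selected.
- **Part A\*:** code treatment as placebo, 3, 5 and 10 mg/kg and report each dose against placebo. Keep a pooled MCS110 estimate only if it is labelled as pooled across doses.
- **Interpretation:** state that these comparisons are partly across study parts. Of the 14 patients at 10 mg/kg in Part B\*, 11 come from Part B, and Part C has no placebo.

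The cost is SAP wording, some degrees of freedom and wider intervals. The standard error for 10 mg/kg against placebo rises by about 6%, and a 6-patient lower-dose arm has one of about 0.17 on the log scale (assumed SD 0.283). No new data are needed.

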7.2 Secondary Endpoint

7.2.1 Bone marker serum C-terminal Type I Collagen peptide (CTX-I) ; Monocytes (hematology); total circulating M-CSF levels; and the soluble form of M-CSFR

To be treated as with all biomarkers. See section 9.

7.2.2 The Joint Range of Motion

The Joint Range of Motion is only assessed for the affected joint and the impairment is recorded.

- Range of motion typically is measured with the neutral-zero method.
- For each plane assessed in the joint, the maximal angle of extension-neutral in degrees or the maximal angle of neutral –flexion in degrees is recorded.
- For the shoulder joint we have the additional planes of abduction to adduction and exterior flexion to interior flexion.

We will present Part A* (i.e., **Part A, Part B and Part C pooled for weeks 1 to 4**) in one set of outputs and further sets of outputs for Part B* and Part C as:

Spaghetti plots will be provided by joint and plane of motion. For example, all knee patients' extension-neutral in degrees vs. time will be plotted in one graph, and their neutral-flexion will be plotted in a separate graph.

In addition all data will be listed showing the baseline, raw value, absolute and percent change from baseline.

7.2.3 Knee and Osteoarthritis Outcome Scale (KOOS) - Parts B and C only

KOOS will only be assessed on the patients whose tumor is in knees.

This measurement was added in after the protocol amendment v03, hence the analysis plan below only applies to the data collected afterwards.

KOOS consists of 5 subscales; Pain, other Symptoms, Function in daily living (ADL), Function in sport and recreation (Sport/Rec) and knee related Quality of life (QOL). The previous week is the time period considered when answering the questions. Standardized answer options are given (5 Likert boxes) and each question is assigned a score from 0 to 4.

A normalized score (100 indicating no symptoms and 0 indicating extreme symptoms) is calculated for each subscale.

Assign the following scores to the boxes:

None	Mild	Moderate	Severe	Extreme
				
0	1	2	3	4

Each subscale score is calculated independently. Calculate the mean score of the individual items of each subscale and divide by 4 (the highest possible score for a single answer option). The normalized score for each subscale is

- PAIN $100 - (\text{Mean Score (P1- P9)} \times 100/4)$, where P1-P9 is questions 1 to 9 for PAIN subscale
- SYMPTOMS $100 - (\text{Mean Score (S1- S7)} \times 100/4)$, where S1-S7 are questions 1 to for SYMPTOMS subscale
- ADL $100 - (\text{Mean Score (A1- A17)} \times 100/4)$, where A1-A17 are questions 1 to 17 for ADL subscale
- SPORT/REC $100 - (\text{Mean Score (SP1- SP5)} \times 100/4)$, where SP1-SP5 are questions 1 to 5 for SPORT/REC subscale
- QOL $100 - (\text{Mean Score (Q1- Q4)} \times 100/4)$, where Q1-Q4 are questions 1 to 4 for QOL subscale

Missing data:

As long as at least 50% of the subscale questions are answered for each subscale, a mean score can be calculated of the data that is present. If more than 50% of the subscale items are omitted, the response is considered invalid and no subscale score should be calculated. For the subscale Pain, this means that at least 5 items must be answered; for Symptoms, at least 4 items; for ADL, 9 items; for Sport/Rec, 3 items; and for QOL, at least 2 items must be answered in order to calculate a subscale score. Subscale scores are independent and can be reported for any number of the individual subscales, i.e. if a particular subscale is not considered valid (for example, the subscale Sport/Rec 2 weeks after total knee replacement), the results from the other subscale can be reported at this time-point.

A total score has not been validated and is not recommended.

Part B

Summary statistics presenting each of KOOS sub scores and absolute change from baseline in each KOOS sub score will be provided with MCS110 arms pooled (Part B*). Panelwise graphs per sub-score will be used, where mean (+/-SE) will be plotted over time with MCS110 arms pooled (Part B*). All KOOS data will be listed by treatment group (defined in Part B).

Part C

Summary statistics presenting each of KOOS sub scores and absolute change from baseline in each KOOS sub score will be provided. Panelwise graphs per sub-score will be used, where mean (+/-SE) will be plotted over time by treatment group. All KOOS data will be listed by treatment group.

7.2.4 Patient Rated Elbow Evaluation (PREE) – Parts B and C only

PREE will only be assessed on patients whose tumor is in elbows.

This measurement was added in after the protocol amendment v03, hence the analysis plan below only applies to the data collected afterwards.

The PREE is a 20-item questionnaire designed to measure elbow pain and disability in activities of daily living. The PREE allows patients to rate their levels of elbow pain and disability from 0 to 10, and consists of 2 subscales:

1) PAIN subscale (0 = no pain, 10 = worst ever)

Pain - 5 items

2) FUNCTION subscale (0 = no difficulty, 10 = unable to do)

Specific activities - 11 items

Usual activities - 4 items

In addition to the individual subscale scores, a total score out of 100 can be computed by equally weighting the PAIN subscale score (sum of five items) and the FUNCTION subscale score (sum of fifteen items, divided by 3).

Computing the Subscales

Pain Score = Sum of the 5 pain items (out of 50). Best Score = 0, Worst Score = 50

Function Score = Sum of the 15 function items, Divided by 3 (out of 50) Best Score = 0, Worst Score = 50

Computing the Total Score

Total Score = Sum of pain + function scores. Best Score = 0, Worst Score = 100

If there is an item missing, the item will be replaced with the mean score of the subscale.

Part B

Summary statistics and graphical displays of total PREE score and absolute change from baseline in PREE score will be provided with MCS110 arms pooled (Part B*). All PREE data will be listed by treatment group (Part B).

Part C

Summary statistics and graphical displays of total PREE score and absolute change from baseline in PREE score will be provided by treatment group. All PREE data will be listed by treatment group.

